Thirty-five individuals volunteers participated in this study, with a mean age of 49.64 years, were 21 women and 14 men. After being selected, the volunteers were allocated to three groups: Neural Mobilization Group (MOB), consisting of individuals with low back pain and treated with the technique, with a total of 18 participants; Neural Mobilization + Medication Group (MOB + MED), constituted by individuals with low back pain, who underwent the mobilization technique associated with medication, a total of 12 participants; and the control group (CONTROL) constituted by healthy individuals without any kind of injury or pain complaint who received the application of the neural mobilization technique, with a total number of 5 participants.

After fulfilling the eligibility criteria, a clinical evaluation and assessments of pain and mobility were carried out, and a quality of life questionnaire was applied (details below).

In order to preserve the accuracy of the intervention effectiveness, participants who missed more than two sessions were excluded from the study. All subjects were assessed by a blinded evaluator. Both participants and evaluator were encouraged not to discuss the received intervention.

First, all personal data from each subject were obtained. Age, body mass, height, profession, school education. After this first step, the participants were submitted to two evaluations, prior to and at the end of the therapeutic program. Both to assess the pain

intensity and to assess the mobility of the lumbar spine, as well as the application of a quality of life questionnaire. A follow up was done thirty days after the end of the treatment to verify the effect of the protocol after the patients return to the normal daily life activity. A characterization and physical examination card were used for a better analysis of the volunteers. The subjects in all three groups were submitted to the same evaluation protocol.

A visual analogue scale (VAS) was used for the assessment of pain intensity, which consists of a line ranging from 0 to 10, where zero characterizes absence of pain and ten, worst pain. After clarifying how to complete the scale, the volunteer was asked to mark a point on the line that indicated the intensity of pain that he or she was feeling at moment of the evaluation [9].

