The Neural Mobilization technique was performed by the same physiotherapist, from the first to the last session, on interleaved days. The protocol of the technique consists in applying a total number of 10 interventions in each patient, with a total duration of 10 minutes, divided into four series of 2 minutes with a 30-second interval between each series according to the protocol proposed in 2012 by Santos et al [15].

The technique was applied with the participant seated in a suitable chair, with a flexed hip (90) and extended knees (figure 1). Next, the physiotherapist applies the technique only to the lower limb in which the individual presents some impairment due to low back pain, observed in the previous physical examination, or in case of absence of irradiation for any of the limbs, the technique was applied only to the right lower limb according to Santos et al 2012 [15].

In the period from July 2016 until September 2017, we screened 60 subjects for eligibility but only 35 individuals had finished all the study protocol according to the includes and exclude criteria. Next, in figure 2 we have a flowchart about the study design, that explain all the procedures realized with the volunteers in all groups.

The statistical analysis was the ANOVA test with repeated measures for the time factor were performed to test between-group differences (followed by the Tukey-Kramer post hoc test), and a paired t test was performed to test within-group differences. The level of significance for the statistical analysis was 5% ($p \le 0.05$), using the standard error as mean \pm SEM [16].

RESULTS:

A total of 35 patients concluded the study and were analyzed. Characteristics of participants included in each group were presented in Table 1 and were homogenous for age at baseline. After the application of the Neural Mobilization technique, the patients were reassessed and the data obtained in both, the initial and final evaluation were submitted to statistical analysis.

Visual Analogue Scale:

Our results demonstrated an improvement in pain in patients treated with neural mobilization. There was a mean reduction in the VAS scale from average 8.47 to 4.05, which was statistically significant in group MOB (Figure 3).

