The decrease of pain sensitivity started at the 4th session for patients treated with neural mobilization only (MOB) and from the 5th treatment session for the patients using medicament plus therapeutic treatment group (MOB + MED). The improvements remained until the end of the treatment (Figure 3).

EVA was 1.5 for MOB group and 2.6 for MOB+MED thirty days after the end of the sessions. Control group (CONTROL), composed of individuals without any kind of pain or injury and who were treated with the neural mobilization technique, it was noted pain intensity on the VAS scale remained at zero until the follow up evaluation (Figure 3).

It should be mentioned that it was not possible to observe a statistically significant difference between the MOB and MOB + MED groups, which suggests that the Neural Mobilization technique alone can improve the pain of these individuals, and it could be considered an adjuvant therapy to the drug treatment of patients (Figure 3).

Roland-Morris Disability Questionnaire (RMDQ):

By adding the yes answers and reaching a value equal to or lower than 10 points, it shows that the person with low back pain presents without some kind of disability, that is, despite the pain, there is no impeding the accomplishment of their daily life tasks. However, if the total varies between 11 and 14 yes / indicated alternatives, it indicates a mild or moderate inability of this individual to perform their daily activities. When the positive responses are equal to or greater than 15, it indicates that this individual has a severe disability [12].

In the MOB group, 17 individuals were evaluated. In the initial measurement, we observed that 15 individuals presented in the normal parameter, not showing any kind of incapacity in performing daily life activities. Two individuals from the same group, presented, in the initial measurement, a severe incapacity to perform the activities of daily living. At the end of the treatment, this questionnaire was reapplied, and 16 of the subjects presented normal parameters, and one of the individuals with severe disability returned to normal levels; the other individual who also presented a severe level of disability, partially reversed their condition, going to mild/moderate disability when performing activities of daily living (Table 2).

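### A non-significant MOB versus MOB + MED comparison is read as evidence for mobilization, but every group received mobilization

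*Combined protocol and SAP*

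**What the plan says.** All references are to the Combined protocol and SAP.

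- **Groups (Materials and Methods).** MOB is 18 patients with low back pain treated with the technique. MOB + MED is patients "who underwent the mobilization technique associated with medication, a total of 12 participants". The control group is healthy, pain-free people "who received the application of the neural mobilization technique, with a total number of 5 participants".
- **Analysis (end of Materials and Methods).** An "ANOVA test with repeated measures for the time factor were performed to test between-group differences", followed by Tukey-Kramer, with paired t tests within groups at the 5% level. No equivalence or non-inferiority margin is given.
- **Before-after result (Results, Visual Analogue Scale).** "There was a mean reduction in the VAS scale from average 8.47 to 4.05", reported as significant in MOB.
- **30-day result (same section).** "EVA was 1.5 for MOB group and 2.6 for MOB+MED thirty days after the end of the sessions". Control VAS stayed at zero.
- **Inference (same section).** The null result is given as the reason: "not possible to observe a statistically significant difference between the MOB and MOB + MED groups, which suggests that the Neural Mobilization technique alone", the text argues, relieves pain. Of the technique it adds that "it could be considered an adjuvant therapy to the drug treatment of patients".

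The Discussion and Conclusion repeat the adjunct claim. The Discussion also acknowledges that MOB + MED patients were more disabled than MOB patients.

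**The concern.** The sentence offers a between-group result as its reason for believing that "the Neural Mobilization technique alone can improve the pain of these individuals". A between-group comparison supports a treatment only if the groups differ in that treatment, and here both sides received it. The adjuvant clause needs medication with mobilization set against medication without it, and no such pair of groups is described.

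A second weakness is independent of the first. Failing to find a difference between 18 and 12 patients, with tests built only to detect differences, does not show that the two groups fared the same.

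The document calls the trial randomized and controlled, so a reader may take the sentence as controlled evidence of efficacy. Without it, the efficacy claim rests on a before-after change, which cannot be separated from natural course, attention or regression to the mean.

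**Working it through.** **1. What the comparison varies**

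| Group | n | Low back pain | Mobilization | Medication as part of group definition |
|---|---|---|---|---|
| MOB | 18 | yes | yes | no |
| MOB + MED | 12 | yes | yes | yes |
| Control | 5 | no | yes | no |

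The sizes reconcile with the stated total: 18 + 12 + 5 = 35. Patients with pain who did not receive mobilization: 0 of 30. Mobilization is on both sides of MOB versus MOB + MED, so no sample size turns that contrast into a test of it. The healthy group cannot fill the gap. It was also mobilized, and a VAS fixed at zero shows neither a treatment effect nor the natural course of pain.

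**2. What the before-after change shows**

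Reading 4.05 as the end-of-treatment mean in MOB:

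- fall during treatment: 8.47 - 4.05 = 4.42
- further fall in the 30 days after sessions ended: 4.05 - 1.5 = 2.55
- total: 8.47 - 1.5 = 6.97, of which 2.55/6.97 = 37% came with no sessions given.

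A delayed effect and natural course cannot be told apart in these data.

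**3. How imprecise the null result is**

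The document states no difference, interval or VAS SD for MOB versus MOB + MED, so there is no figure to reproduce. The time point of the null result is not stated either. The 30-day means give 2.6 - 1.5 = 1.1 (MOB + MED minus MOB). SDs of 2.0 and 2.5 are assumed. Figure 3 plots mean ± SEM and may allow the real SD to be derived, but it is not shown in the text reviewed.

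Half-width = critical value × SD × √(1/18 + 1/12), where the root is 0.3727. The critical value is 2.048 unadjusted (t, 28 df), or 2.457 for Tukey (three groups, 32 df).

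| Assumed SD | Unadjusted 95% CI | With Tukey critical value |
|---|---|---|
| 2.0 | 1.1 ± 1.53: -0.4 to 2.6 | 1.1 ± 1.83: -0.7 to 2.9 |
| 2.5 | 1.1 ± 1.91: -0.8 to 3.0 | 1.1 ± 2.29: -1.2 to 3.4 |

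Most of each interval favours MOB, but none of it bears on mobilization versus no mobilization.

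**4. Whether the two pain groups were alike**

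Baseline counts come from Tables 1 to 3 and the RMDQ text. All tests are post hoc.

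| Baseline feature | MOB | MOB + MED | p |
|---|---|---|---|
| ODI 0-20% | 7/16 | 0/11 | 0.022 (Fisher) |
| ODI 41% or above | 2/16 | 3/11 | 0.37 (Fisher) |
| ODI, all bands | 7/7/1/1 | 0/8/3/0 | 0.034 (exact rank-sum) |
| RMDQ 0-10 | 15/17 | 6/11 | 0.076 (Fisher) |
| Full- or part-time work | 17/18 | 4/12 | 0.0006 (Fisher) |
| Men | 7/18 | 5/12 | 1.0 (Fisher) |

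Mean age was almost identical (43.4 and 43.3 years). The ODI result depends on the cut, but the direction agrees with the Discussion. The contrast is therefore not a clean test of medication either.

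**The case against.** The strongest reply is that the Conclusion does not rely on the null comparison. It rests effectiveness on initial versus final evaluation and on change between sessions, so deleting the sentence would leave it standing. The sentence is also hedged, and a milder reading exists: both groups improved, and no added benefit of medication was detected.

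The first part is right about the Conclusion's stated basis. But the Conclusion calls the technique effective without saying that the change is uncontrolled, and the adjunct claim recurs there and in the Discussion. The milder reading would be defensible had it been written. As written, the null result is the reason given for a claim about mobilization, and hedging does not make the contrast informative.

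Three lesser points stand as limits:

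- The intervals use assumed SDs and a single-time-point formula, not the repeated-measures model. They illustrate imprecision only.
- The 37% figure assumes that the same patients gave the final and 30-day values; no n is given for the latter.
- Regression to the mean from the entry rule alone (VAS at least 4) is probably small. Suppose baseline VAS is a normal distribution cut off at 4 with observed mean 8.47, so that 8.47 = μ + SD × φ(a)/(1 - Φ(a)), a = (4 - μ)/SD. An SD of 2.0 gives μ = 8.40 and 2.5 gives 8.22, so at most 0.07 or 0.25 of the 4.42-point fall. The scale's ceiling at 10 makes this rough. Enrolment during a flare could add more, and the documents cannot size that.

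**Conclusion.** The concern holds. The MOB versus MOB + MED comparison gives no evidence on mobilization, because 0 of 30 patients with pain went without it. This follows from the group definitions and needs no assumed figure. The adjuvant claim is untested for want of a medication-only group.

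The null result also fails to establish that the two groups did equally well. There is no margin, the groups differed in baseline ODI and employment, and at an assumed SD of 2.0 to 2.5 the unadjusted interval extends 1.5 to 1.9 points either side of the 1.1-point gap. This supporting argument depends on those SDs.

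The fall in MOB is not in dispute. It is an uncontrolled change, and it is the only support in these data for a statement about mobilization alone. The data stand; what may be concluded from them is narrower. This should be corrected.

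**What to change.** 1. Replace the sentence in the Visual Analogue Scale results with wording such as:

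   > VAS did not differ significantly between MOB (n = 18) and MOB + MED (n = 12) at [time point]; the difference was X (95% CI L to U). Both groups received mobilization, so this comparison does not test mobilization, and it does not show that the groups were equivalent.

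2. Delete the adjuvant clause or mark it untested, and treat its repeats in the Discussion and Conclusion the same way.
3. Rest any statement about mobilization alone on the before-after change, called uncontrolled, both here and in the Conclusion.
4. Report the MOB + MED minus MOB difference at the final and 30-day evaluations with a 95% CI adjusted for baseline VAS, as a description of non-comparable groups. An ODI-adjusted version is exploratory only: ODI is available for 16 + 11 = 27 of 30 patients, overlap is limited and confounding will remain.

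The cost is rewording plus one small re-analysis of data in hand. The estimate will still be imprecise and confounded, and the report will have no between-group evidence for mobilization. Evidence of that kind would need patients with low back pain who do not receive it.

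Two related but separate points can be settled in the same edit: reconcile the randomized label with the description of allocation and the healthy control group, and mark the Discussion's statement about reduced medication as untested.

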The Portuguese version of the Roland - Morris Disability Questionnaire (RMDQ) [10] was applied to the subjects of the study. The questionnaire consists in assessing the severity and level of physical disability induced by low back pain through 24 alternatives with dichotomic answers (yes or no). The questionnaire must be self-filled by the volunteers, demonstrating their success or difficulty in performing their daily life tasks associated with their pain, and the final result of the questionnaire is the sum of the yes or the marked responses. As some patients had some difficulty reading or understanding the instructions of the questionnaire, the reading was done together with the researchers.

It was applied the Oswestry Disability Index (ODI) version 2.0, validated in 2007 by Vigatto et al [11]. The scale consists on a list of ten questions with six possible answers, each answer has a score ranging from 0 to 5, in the order in which they are listed, that is, the first value is 0 and the last value is 5. The first question assesses the intensity of the pain and the others assess the effect caused by the pain on the performance of activities of daily living, like personal cares, dress up, sleep and so forth [12].

To analyze the total score obtained in this questionnaire, there is a mathematical formula that can be used. After adding all the results marked by the individuals in the questionnaire were used a mathematical formula to calculate the total score obtained in percentage for each volunteer. The total score is divided by the number of answered questions divided by 5. The result of this division is multiplied by 100 and the final values are given in percentages, thus ([score \div (number of answered questions X 5)] X 100)[12].

In order to evaluate the mobility of the lumbar spine, the 3rd finger to the ground distance test was used. This test consists of an active test, where the individual is placed in an orthostatic position, with the feet separated in the hip line, keeping knee extended and heel leaning on the ground, then the participant is asked to perform a trunk flexion with the arms extended and try to bring his hand closer to the ground. Then, using a tape measure, the

distance between the tip of the 3rd finger and the ground is measured, and the value given in centimeters (cm) is considered as the mobility of the volunteer lumbar spine [13] [14].

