In the MOB + MED group, eleven individuals were evaluated. In the initial measurement, we observed that 6 individuals presented in the normal parameter; 3 subjects had mild / moderate disability and 2 individuals from the same group, presented, in the initial measurement, a severe incapacity to perform the activities of daily living. After the end of the treatment, the questionnaire was reapplied, and 9 of the individuals presented in the normal parameter. Three of the individuals with some degree of disability, returned to normal levels

and only 2 individuals who had a severe level of disability did not improve their disability when performing activities of daily living (Table 2).

In the control group (CONTROL), composed of 5 healthy individuals, with no complaints of low back pain and without injury, initially they had normal parameters, and did not present any type of disability when performing daily life activities, after the application of the proposed protocol (Table 2).

The Oswestry Disability Index (ODI):

In the initial measure (I) of the ODI were assessed after the application of the mathematical formula to evaluate the level of incapacity of the individuals. The first application of ODI can be classified into five levels of disability. The first stage classified in 0-20%, characterizes a minimal disability. The second stage in the range of 21-40%, characterizes a moderate disability. Followed for the range of 41-60%, that characterizes an intense disability. The range of 61-80% characterizes an immobilization. And finally, the range of 80-100%, that means invalidity.

The Final measure (F) of the ODI assessed was the effect of the treatment in the evolution of the clinical condition after the appliance of the mathematical formula. The first stage classifies the evolution in excellent in the range of 0-20%. The range of 21-40% classifies the evolution in great. The range of 41-60%, classifies the evolution in maintenance. The range of 61-100%, classifies the evolution after the treatment as worse.

Comparing the initial and the final measure of the ODI, it can be observed an improvement of the clinical condition of the subjects assessed in both groups, MOB, and MOB+MED. Only the CONTROL group maintained the same results in both measures (Table 3).

Lumbar mobility:

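### The RMDQ is reported only in three bands, with 21 of 28 treated patients already in the best band at baseline, so the counts do not support the improvement claimed for the MOB group

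*Combined protocol and SAP*

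**What the plan says.** All references are to the combined protocol and SAP.

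- **Materials and Methods, RMDQ.** The instrument measures disability "through 24 alternatives with dichotomic answers (yes or no", and "the final result of the questionnaire is the sum of the yes or the marked responses". The outcome is therefore a number from 0 to 24.
- **Materials and Methods, statistical paragraph.** "a paired t test was performed to test within-group differences", at the 5% level. No other within-group test is named, sidedness is not stated, and the disability scales are not excluded.
- **Results, RMDQ.** Totals are cut into three bands. For the lowest the text says "a value equal to or lower than 10 points, it shows that the person with low back pain presents without some kind of disability". For the next, "if the total varies between 11 and 14 yes / indicated alternatives, it indicates a mild or moderate inability". Totals of 15 or more are called severe. The text and Table 2 then give only counts per band; for MOB + MED at baseline, "6 individuals presented in the normal parameter; 3 subjects had mild / moderate disability", with 2 severe. There is no mean, change score, confidence interval or p-value.
- **Results, ODI.** A percentage is computed for each volunteer, but Table 3 shows only bands. The text concludes: "Comparing the initial and the final measure of the ODI, it can be observed an improvement of the clinical condition".
- **Discussion.** The RMDQ is said to show that disability in the MOB group moved from mild to normal in nearly every patient. The two questionnaires together are said to show success in all patients.

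**The concern.** The bands discard the score that the methods define. A fall from 10 limitations to 0 counts as no change, while a fall from 11 to 10 counts as a return to normal. A patient who starts at 10 or below can register worsening but not improvement. If most patients start there, the table says little about whether disability changed, in either direction.

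Functional capacity is a stated aim, and the Discussion draws a favourable conclusion from this table. At stake is whether that conclusion has any support in the RMDQ as reported.

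**Working it through.** **1. Reproduce the counts.** The order is normal / mild–moderate / severe. The severe cell for MOB at baseline is blank in Table 2; the text gives 2.

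| Group | Initial | Final | n |
|---|---|---|---|
| MOB | 15 / 0 / 2 | 16 / 1 / 0 | 17 |
| MOB + MED | 6 / 3 / 2 | 9 / 0 / 2 | 11 |

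The rows sum to 17 and 11 at both times and agree with the text.

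**2. Ceiling.** Already in the best band: MOB 15/17 = 88%; MOB + MED 6/11 = 55%; together 21/28 = 75%. Patients able to improve a band: 2 and 5.

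**3. Best case: everyone above the lowest band moves into it and nobody worsens.** The exact two-sided sign (McNemar) test with k one-way changes gives p = 2 × 0.5^k. For k = 2 this is 0.50, for k = 5 it is 0.0625, and for k = 6 it is 0.031. At least 6 changes are needed; 2 and 5 are available.

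The plan's paired t test, applied to band codes 0/1/2, with d the number of bands gained and t = mean(d) / (SD/√n):

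- MOB: d = 2, 2 and fifteen zeros. Mean 4/17 = 0.235; SD = √[(8 − 16/17)/16] = 0.664; t = 0.235/(0.664/√17) = 1.46; df 16; p = 0.163.
- MOB + MED: d = three 1s, two 2s and six zeros. Mean 7/11 = 0.636; SD = √[(11 − 49/11)/10] = 0.809; t = 0.636/(0.809/√11) = 2.61; df 10; p = 0.026.

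Other two-sided tests: for MOB the most favourable is uncorrected McNemar, p = 0.157. For MOB + MED, uncorrected McNemar gives 0.025 and continuity-corrected 0.074.

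**4. Observed changes.**

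- MOB: one patient went from severe to normal (d = 2) and one from severe to mild/moderate (d = 1). Exact p = 2 × 0.5² = 0.50. Paired t: mean 3/17 = 0.176, SD = √[(5 − 9/17)/16] = 0.529, t = 1.38, p = 0.188.
- MOB + MED: three patients went from mild/moderate to normal; two stayed severe. Exact p = 2 × 0.5³ = 0.25. Paired t: mean 3/11 = 0.273, SD = √[(3 − 9/11)/10] = 0.467, t = 1.94, p = 0.082.

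**5. RMDQ bands against ODI bands at baseline.** ODI of 21% or more, which the Results call at least moderate disability: MOB 7 + 1 + 1 = 9 of 16; MOB + MED 8 + 3 = 11 of 11. RMDQ above 10: 2 of 17 and 5 of 11. The groups are 18 and 12, so at most one patient in each lacks an RMDQ. Patients normal on RMDQ but at 21% or more on ODI therefore number at least 9 − 2 − 1 = 6 in MOB and 11 − 5 − 1 = 5 in MOB + MED.

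**6. Discussion against Table 2.** No MOB patient began in the mild/moderate band, 15 of 17 began as normal, and one moved to normal, from severe. Two severe MOB + MED patients did not improve a band. The wider remark that mild and moderate disability improved fits MOB + MED (3 of 3), but not MOB, which had no such patients.

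**The case against.** The strongest reply is that this is a reporting gap. The methods define numeric scores and a paired t test, nothing says that the bands are the planned endpoint, and no RMDQ p-value is claimed. That stands, and it makes the fix easy: the missing item is the result of the analysis already named. It does not rescue the Discussion, whose statement about MOB contradicts the table.

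Four limits also stand.

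- A reader might infer that neither treated group could have reached p ≤ 0.05. For MOB + MED that rests on an exact two-sided (or continuity-corrected) test which the plan does not name. The named paired t, on band codes, would give 0.026 in the best case. A t test on 11 banded values is a weak choice, but it is the documented one.
- A reader might extend the ceiling to the ODI. There, 9 of 16 and 11 of 11 patients could improve a band, so the smallest exact p is 2 × 0.5⁹ = 0.004 and 2 × 0.5¹¹ = 0.001. Patients at 21% or more fell from 9 to 2 and from 11 to 4. The ODI shares the banded reporting, not the ceiling.
- A reader might take the ODI comparison as proof that the RMDQ cut-point is wrong. It shows only that the two sets of bands disagree. The instruments differ (the ODI includes a pain item), and the source cited for the cut-points cannot be checked here.
- Pooling both treated groups, 5 of 5 changes are improvements: exact p = 0.0625, paired t on band codes 0.031. The plan's test is within group, so this does not replace the group results, but the bands are not wholly silent.

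The RMDQ is also not the only functional measure: lumbar mobility is reported in centimetres with p-values. The only primary endpoint named in either document is the VAS.

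**Conclusion.** The concern holds in a limited form. The defined score is replaced by bands in which 75% of treated patients cannot improve. For MOB, no usual paired test could have reached 5%, even with full recovery of both patients above the lowest band. For MOB + MED, that depends on the test. The observed band change is not significant in either group by any two-sided test tried. The Discussion's RMDQ statement about MOB is contradicted by the document's own counts.

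Assumptions: two-sided testing, the severe MOB baseline count of 2 taken from the text, and groups of 18 and 12. Sidedness matters in one place. Halving the observed MOB + MED paired t gives 0.041, while the one-sided exact value is 0.125. The MOB best case fails either way (0.157/2 = 0.079).

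None of this shows that disability failed to improve. The result on the 0–24 sum cannot be computed, because no RMDQ means or SDs are given. This should be fixed, but it does not touch the VAS result.

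**What to change.** - Analyse the RMDQ 0–24 sum, and likewise the ODI percentage, as paired change (final minus initial) in each treated group, with the mean or median change, a 95% confidence interval, and a paired t or Wilcoxon test. State sidedness.
- Keep Tables 2 and 3 as description. Do not present RMDQ totals of 0–10 as absence of disability without addressing the disagreement with the ODI bands.
- State why the RMDQ has 17 and 11 patients, and the ODI 16 and 11, when the groups are 18 and 12.
- Correct the Discussion: remove the statement that nearly all MOB patients moved from mild to normal, do not claim RMDQ improvement from band counts, and qualify the statement about success in all patients.

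The cost is a small re-analysis of scores already collected, plus wording changes. The conclusion on disability may turn out less favourable than the present one.
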